8 ANALYSIS SETS

The main population for non-safety analyses will be the Full Analysis Set.

Safety will be analyzed using the Safety Set.

8.1 Full Analysis Set

The Full Analysis Set (FAS) will consist of all enrolled patients in the SC arm who have signed the ICF and who have at least one valid non-safety assessment after enrollment as well as all patients randomized to the CIG or IQOS arm who have signed the ICF, have at least one valid non-safety assessment after randomization and have at least one post-randomization product (IQOS or CIG) use experience. The FAS will be analyzed by enrolled arm (randomization arm for CIG or IQOS, or SC arm) and by product use category (see section 5.7).

Confidentiality Statement

Data and information contained in this document are considered to constitute trade secrets and confidential commercial information, and the legal protections provided to such trade secrets and confidential information are hereby claimed under the provisions of applicable law. No part of this document may be publicly disclosed without the written consent of Philip Morris Products S.A

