5.2.1 Discontinuation from the study

Patients must be discontinued from the study for any of the following reasons:

- Withdrawal of informed consent.
- Discontinuation is considered to be in the interest of the patient from a safety perspective as judged by the Investigator.
- Positive or unclear pregnancy test.
- The Sponsor or Investigator terminates the study or the study terminates at a particular investigational site. If the Sponsor or the Investigator decides to prematurely terminate the study, the patient will be promptly informed. The investigational site/head of the medical institution should report the fact and the reason in writing to the IRB / IEC.
- Patient has to undergo open surgical AAA treatment or AAA endovascular repair (as per the treating physician's decision based on the standard of care as documented in the Guidelines for Diagnosis and Treatment of Aortic Aneurysm and Aortic Dissection¹).
- The patient experiences a rupture of his/her AAA.
- Patient becomes an employee of the investigational site, a tobacco company or any other parties involved in the study.
- Lost to follow-up.

Patients may be discontinued from the study for the following reasons:

- Non-compliance to the study procedures based on the judgment of the Investigator.

If a violation of selection criteria is detected after enrollment, patients might be discontinued from the study based on a case-by-case decision of the Investigator.

Confidentiality Statement

Data and information contained in this document are considered to constitute trade secrets and confidential commercial information, and the legal protections provided to such trade secrets and confidential information are hereby claimed under the applicable provisions of applicable law. No part of this document may be publicly disclosed without the written consent of Philip Morris Products S.A.

Patients will not be discontinued from the study for the use of tobacco or nicotine-containing products other than their assigned product/regimen unless judged by Investigator.

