7.2 Advice on the Risks of Smoking/SC Advice

All patients, screened for the study will be first advised that the best way of preventing further AAA disease progression is to stop smoking and will be given advice on risk of smoking and SC advice at V1.

From V1 onwards, all patients screened to be enrolled into CC, IQOS and SC arms will receive information on the risks of smoking, and the advice to quit smoking or to be abstinent from smoking will be given to all patients as described in Appendix 1 – Schedule of Events. This will take the form of a brief interview according to WHO recommendations ³⁹.

Any patient who is willing to attempt quitting CC or IQOS or use of any tobacco or nicotine-containing products at any time during the study will be encouraged to do so. He/She will be referred to appropriate medical services, and the standard of care to support SC will be applied.

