9.2 Baseline Visit: V2

Table 5 shows the assessments that will be performed at Baseline Visit (V2): all the assessments described below have to be conducted in all patients unless specified otherwise. All the samples will be collected, stored, and shipped according to the laboratory/sample handling manual.

Table 5 Time Schedule – Baseline Visit: V2

Time	Sample collection	Procedures	Additional information
Start of procedure			
Start of the visit			Advice on the risks of smoking/SC advice
Prior to enrollment		Re-check of applicable eligibility criteria	
		CT scan assessment for eligibility	Made at V1, sent to the central reading site for assessment, to be checked at V2 for eligibility.

Confidentiality Statement

Data and information contained in this document are considered to constitute trade secrets and confidential commercial information, and the legal protections provided to such trade secrets and confidential information are hereby claimed under the applicable provisions of applicable law. No part of this document may be publicly disclosed without the written consent of Philip Morris Products S.A.

Time	Sample collection	Procedures	Additional information
Start of procedure			
		Spot urine for pregnancy and cotinine tests	Pregnancy test (all females, except when menopause is confirmed): at the study site. Cotinine test: test at the study site. The cut-off value of urine cotinine test in all smoking patients: ≥ 200 ng/ml, in all former smokers: < 100 ng/ml.
		Intention to quit smoking in the next 6 months after having been advised to quit smoking	Smoking patients only
		Concomitant medication	
		Follow-up on concomitant diseases (ongoing or not)	
		Assessment of concomitant diseases	
		Readiness to comply to study procedures	
		Judgment on eligibility	
Enrollment		Enrollment of eligible patients for the IQOS and CC arm in IXRS	Smoking patients only.
		Enrollment of eligible patients into the SC arm in IXRS	Former smoker patients only.
After enrollment		Distribution of the diary for tobacco or nicotine-containing product use self-reporting	Patients will be provided with information on how to fill the diary
	U	Spot urine collection for collection of samples for total NNN, total NNAL, CEMA, NEQ, creatinine	
	B/U	Blood/Urine: Hematology, clinical chemistry, urine analysis	Blood samples have to be taken after at least 10 hours of fasting.

Confidentiality Statement

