Data and information contained in this document are considered to constitute trade secrets and confidential commercial information, and the legal protections provided to such trade secrets and confidential information are hereby claimed under the applicable provisions of applicable law. No part of this document may be publicly disclosed without the written consent of Philip Morris Products S.A.

Time	Sample collection	Procedures	Additional information
Start of procedure			
		Clinical assessments:	
		Vital signs	Vital signs: at least 15 min after having smoked CC or used IQOS. Systolic and diastolic blood pressure also assessed as cardiovascular risk factors
		Physical examinations	
		Body weight	Assessed as cardiovascular risk factor
		Waist circumference	Assessed as cardiovascular risk factor
		AE/SAE recording	
		Debriefing on IQOS	Smoking patients only.
		Randomization	Smoking patients only
		Patients are informed of their randomized study arm.	Smoking patients only
		Distribution of the IQOS supplies as per site process	Smoking patients randomized to IQOS arm only
		Any other assessment as per standard of care for AAA patients and deemed necessary by the Investigator	
End of the visit			
After check out		Patients start using their allocated product	IQOS and CC arm only

Abbreviations: AAA = Abdominal Aortic Aneurysm; AE = Adverse event; ; B = Blood/Plasma; CEMA = 2-Cyanoethylmercapturic Acid; CT = Computed Tomography; NEQ = nicotine equivalents, consisting of the molar sum of free nicotine, nicotine-glucuronide, free cotinine, cotinine-glucuronide, free trans-3'-hydroxycotinine and trans-3'-hydroxycotinineglucuronide; NNAL = 4-[methylnitrosamino]-1-[3-pyridyl]-1-butanol; NNN = N-nitrosonornicotine; SAE = Serious adverse event; SC = Smoking Cessation; U = Urine; .

Confidentiality Statement

Data and information contained in this document are considered to constitute trade secrets and confidential commercial information, and the legal protections provided to such trade secrets and confidential information are hereby claimed under the applicable provisions of applicable law. No part of this document may be publicly disclosed without the written consent of Philip Morris Products S.A.

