12.4.1 Full Analysis Set (FAS)

The Full Analysis Set (FAS) will consist of all enrolled patients in the SC arm who have signed the ICF and who have at least one valid non-safety assessment after enrollment as well as all patients randomized to the CC or IQOS arm who have signed the ICF, have at least one valid non-safety assessment after randomization and have at least one post-randomization product (IQOS or CC) use experience. The FAS will be analyzed by enrolled arm (randomization arm for CC or IQOS, or SC arm).

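### The Full Analysis Set uses a different entry rule for SC than for IQOS and CIG, and its product-use condition drops randomised patients who quit at V2

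*SAP*

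**What the plan says.** SAP 8.1 sets two rules. For SC, the FAS takes "all enrolled patients in the SC arm who have signed the ICF and who have at least one valid non-safety assessment after enrollment". Patients randomised to IQOS or CIG (CC in the protocol) must, besides signing consent, "have at least one valid non-safety assessment after randomization and have at least one post-randomization product (IQOS or CIG) use experience". Protocol 12.4.1 has the same two rules, so the SAP did not introduce the difference.

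Table 5 (Protocol 9.2) gives the V2 order. The block after enrollment contains "Spot urine collection for collection of samples for total NNN, total NNAL, CEMA, NEQ, creatinine", then safety samples, vital signs, weight and waist. Randomization comes lower down, followed by the row "Patients are informed of their randomized study arm". SAP 9.1.4 defines baseline accordingly: the last assessment before randomization in IQOS and CIG, the V2 assessment in SC.

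Three other provisions matter:

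- **Quitting.** Under Protocol 7.2, a patient willing to stop "at any time during the study will be encouraged to do so".
- **Discontinuation.** Protocol 5.2.1 ends participation when repair is needed and when "The patient experiences a rupture of his/her AAA".
- **Analysis by arm.** Protocol 12.3 and SAP 4.3.3 keep patients whose smoking habits change in their randomised arm for the analysis.

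**The concern.** Membership of the main analysis set should depend on what is known when a patient enters an arm. Here it depends on later behaviour and later data in two arms, and possibly on nothing beyond the baseline visit in the third.

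The repair and rupture rates, the Kaplan-Meier curves and the growth-threshold counts (SAP 9.5.2.1.1 to 9.5.2.1.3) all use the FAS by arm. If the rule removes early losses from IQOS and CIG but keeps them in SC, comparisons with SC rest on unequal inclusion. If it removes immediate quitters, the randomised comparison is no longer of the groups as randomised. The study is open-label, so behaviour after a patient learns the assigned arm may be related to that arm.

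**Working it through.** **1. What V2 data can do for each arm**

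| | SC | IQOS and CIG |
|---|---|---|
| Reference point (SAP 8.1) | enrollment | randomization |
| V2 biomarker urine, weight, waist (Table 5) | listed after the reference point, so can qualify | listed before it, so cannot |
| First scheduled qualifying visit | V2 | V3, about 6 months later (Protocol 9.3) |
| Product-use condition | none | at least one use of IQOS or a cigarette |

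**2. Immediate quitter.** This step needs no inference about visit order. A randomised patient stops at V2, uses neither product and attends V3 to V8 with all scans. The assessment clause is met and the product-use clause fails, so the patient leaves the FAS. The patient's slope leaves the primary analysis, and the patient also drops out of the FAS summary for the smoking-abstinence category of SAP 5.7.

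**3. Loss before V3.** Table 7 (Protocol 9.4) lists pregnancy urine, safety laboratory tests, ECG, physical examination and event recording. It lists no CT, biomarkers, weight, waist or diary. SAP 9.5.2.1.2 starts person-time at randomization, so months 0 to 6 are meant to count. Whether such a patient qualifies turns on what a valid non-safety assessment is, and neither document defines it. There are two main candidates:

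- **Diary** (Protocol 7.9). The first questionnaire falls one month after V2, but diaries are collected from V3 onwards and Table 7 lists no collection.
- **Diameter at the repair decision** (Protocol 7.4.9). A centrally read value goes into the CRF. This covers repair and not rupture, and the section does not say that a new scan is required.

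**4. Illustration of the worst case.** The plan has no figure to reproduce: it gives no arm sizes, event rates or FAS counts. Assume a constant hazard L per year, equal in all arms, 3 years of follow-up, every event before 0.5 years lost from the randomised arms, and none lost from SC.

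- Probability of an event in the remaining 2.5 years: q = 1 − exp(−2.5L)
- Expected randomised rate after the loss: q / (0.5 + q/L)
- Ratio to SC: that rate divided by L
- Share of 3-year events lost: (1 − exp(−0.5L)) / (1 − exp(−3L))

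For L = 0.10: q = 0.2212; rate = 0.2212 / (0.5 + 2.212) = 0.0816; ratio = 0.816.

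| L (assumed) | Share lost | Randomised rate | Ratio to SC |
|---|---|---|---|
| 0.02 | 17.1% | 0.0166 | 0.83 |
| 0.05 | 17.7% | 0.0412 | 0.825 |
| 0.10 | 18.8% | 0.0816 | 0.816 |
| 0.20 | 21.1% | 0.1595 | 0.797 |
| 0.30 | 23.5% | 0.2336 | 0.779 |

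With one rule for all arms the expected ratio is 1.00.

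In a small arm one patient matters more. Assume 10 patients per arm, events at 3 and 18 months, and the rest followed for 3 years. SC gives 2 / (0.25 + 1.5 + 24) = 2/25.75 = 0.078 per person-year. A randomised arm that loses the early event gives 1 / (1.5 + 24) = 1/25.5 = 0.039, about half.

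**5. Chance that the quitter clause applies.** Protocol 4.4 reports 32 enrolled without a split by arm. Assuming two thirds are randomised (about 21), the chance of at least one immediate quitter is 1 − (1 − p)^21: 35%, 66% or 89% for assumed p of 2%, 5% or 10%.

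**The case against.** A reader might infer that early repairs and ruptures are certain to vanish from IQOS and CIG. The documents do not support that. A repair decision before V3 brings a recorded diameter, diaries may exist from month 1, assessments at unscheduled visits are documented (Protocol 4), and the repair-decision and rupture dates are themselves named endpoints (SAP 3.2). Any of these might count. This stands: early loss is possible, and most plausible for rupture, death or withdrawal soon after V2. It does not settle the matter, because nothing says which of them count, and SAP 9.1.6 keeps unscheduled data out of the tables.

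Other points on that side:

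- **Order within V2.** Protocol 9 allows procedures without a start time at any point in the day, so SC entry on V2 data is an inference from Table 5, though the baseline definitions in SAP 9.1.4 agree with it.
- **Quitters are few.** Randomised patients smoke more than 5 cigarettes a day and state no intention to quit within 6 months, rechecked at V2. One cigarette afterwards qualifies them. This limits how often the clause applies; it does not justify it.
- **No literal contradiction.** Protocol 12.3 and SAP 4.3.3 say in which arm a patient is analysed, not who is in the set. That is fair. The exclusion still depends on behaviour after randomization.
- **Visibility.** SAP 9.2 plans FAS exclusions with reasons by arm, and ruptures should appear among Safety Set adverse events, since Protocol 8.1.1 does not exempt them by name. This helps a reader see the exclusions but does not put the events back into the incidence analysis.

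**Conclusion.** The entry rule differs by arm, and the product-use clause excludes randomised patients on later behaviour. Both follow from the text. Loss of early events from the randomised arms is possible and depends on an undefined term.

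The effect falls mainly on person-year incidence and Kaplan-Meier comparisons with SC. Two wider inferences are not supported:

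- **That the primary slope is generally compromised.** It uses V3 to V8 scans in every arm, so anyone with a slope already meets the assessment clause. Only immediate quitters are affected.
- **That IQOS is favoured over CIG.** They share one rule, so bias between them needs unequal quitting or unequal early loss.

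Nor should the effect be read as head counts over arm size. Repair and rupture are planned as events per person-year and by Kaplan-Meier. Under SAP 9.1.3, an SC patient without post-baseline scans would not dilute a percentage based on non-missing values.

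No size can be given from the documents. The ratios of 0.83 to 0.78 and the halving in a 10-patient arm are worst-case illustrations that rest on assumed hazards, arm sizes and complete loss of pre-V3 events. The study is descriptive and SC is not randomised, so this is an inexpensive improvement that should be made rather than a flaw that invalidates the plan.

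**What to change.** - In SAP 8.1, define the FAS as all patients randomised to IQOS or CIG and all patients enrolled in SC at V2, with no product-use or post-baseline-assessment condition. Record this in SAP 7 as a change from Protocol 12.4.1.
- In SAP 9.5.2.1.2, count repair-decision and rupture dates and person-time from V2 in all arms. SC has no randomization date, although the formula uses one. Randomised patients are randomised at V2, so their clock does not move.
- In SAP 9.5.2.1.1, the planned clock from diagnosis can stay; only membership of the set changes.
- Keep slopes and visit summaries on patients with data, and show n.

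The cost is SAP rewording, one derivation flag and a stated departure from the protocol's FAS wording. A few patients may be in the FAS with no post-baseline data. No new data are needed. If the SAP can no longer be amended before database lock, SAP 1 provides for describing the change in the clinical study report.

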8.2 Safety Set

Safety Set consists of all the patients enrolled with signed ICF who have at least one valid value for a safety assessment during the course of the study. The Safety Set will be analyzed by enrollment arm and in patients exposed but not randomized.

8.3 Protocol Deviations

All protocol deviations will be entered into the Clinical Trial Management System (CTMS) or other approved format.

Information from the source documents will represent the primary source of protocol deviations. Information following site monitoring and other manual reviews will be documented in the site visit reports, follow-up letters, audit documentation, or other manual review and will be recorded and tracked in the CTMS or other approved format. Telecommunications and other verbal communications regarding deviations will be considered and handled as important communication, and documented and tracked as protocol deviations, as necessary.

Classification of the protocol deviation will be decided before the database lock during the pre-analysis data review meeting. Protocol deviations will be summarized and listed. All protocol deviations will be reviewed to determine their severity/impact when subjects are assigned to analysis sets. Each deviation will be classified as major or minor. All major deviations will be further reviewed to determine whether or not the deviation impacts the evaluability of the results and therefore should result in the subject being excluded from an analysis set.

The categories for the major protocol deviations will include, but are not limited to, the deviations presented in Table 3.

Table 3 Definition of Major Protocol Deviations

Category	Description
Mis-randomization	Being administered the wrong product according to the randomization schedule
Violation	Violation of inclusion/exclusion criteria
Product adherence	Non-adherence in the IQOS and SC arms will be defined per subject. It will be based on product use reported in the diaries. Product use categories will be defined on top of the randomization arm (see section 5.7).

Confidentiality Statement

Data and information contained in this document are considered to constitute trade secrets and confidential commercial information, and the legal protections provided to such trade secrets and confidential information are hereby claimed under the provisions of applicable law. No part of this document may be publicly disclosed without the written consent of Philip Morris Products S.A.

The categories for the minor deviations will include, but are not limited to, the deviations presented in Table 4.

Table 4 Definition of Minor Protocol Deviations

Category	Description
Procedural violation	Violation of planned procedure
Visit window deviation	Visits outside of visit window
Time missing	Assessment date or time is missing
Assessment missing	Assessment is missing
Visit missing	Scheduled visit not done

9 PLANNED STATISTICAL METHODS

9.1 General Considerations

9.1.1 Stratified Presentation

As described in Section 7, stratified analyses will not be conducted as part of this SAP.

9.1.2 Sub-group Analyses

Not applicable.

9.1.3 Descriptive Statistics

Data will be presented in listings, enrollment arm, patient, and study visit, unless otherwise specified.

For continuous data, summary statistics will include the number of patients with non-missing values [n], number and percent of patients with missing data, the mean and standard deviation (SD), median, first and third quartiles, minimum and maximum, and 95% confidence interval (CI). Log-normally distributed data (e.g., BoExp data) will also include the geometric mean and coefficient of variation (CV) in addition to the mean and SD. Post-baseline summaries will include change from baseline apart from log-normal variables which will present % change from baseline (see Section 5.1.2).

Confidentiality Statement

Data and information contained in this document are considered to constitute trade secrets and confidential commercial information, and the legal protections provided to such trade secrets and confidential information are hereby claimed under the provisions of applicable law. No part of this document may be publicly disclosed without the written consent of Philip Morris Products S.A.

For categorical data, frequency counts and percentages will be presented. Percentages of missing values will be computed using the number of patients [N] included in the corresponding group in the denominator, while percentages related to ‘non-missing’ categories will be computed using the number of patients with non-missing values in the denominator.

9.1.4 Definitions for Statistical Data Analysis

In general, baseline value for any given variable will be the last assessment prior to randomization for the patients randomized to either IQOS or CIG smoking. For the patients in the SC arm, baseline value for any given variable will be the assessment of any given variable performed at V2 (e.g., CT scan made at V1 and assessed by the central reading site and available at V2).

9.1.5 Handling of Dropouts or Missing Data

For BoExp parameters:

- Values below the lower limit of quantification (LLOQ) will be imputed using LLOQ/2. For values above the upper limit of quantification (ULOQ), the ULOQ will be imputed.
- The number and percentage of values below LLOQ or above ULOQ will be presented in each summary table (the percentage of values below LLOQ/ULOQ will use the number of patients with non-missing values in the denominator). If more than 50% of the data are below LLOQ, only the number and percentage of values below LLOQ will be reported in the summary together with the minimum and maximum values.

For self-reported tobacco or nicotine-containing product use:

- Only available data will be included in the product use summaries.

